9.2 Valacyclovir⁹¹

Proper name: Valacyclovir (as valacyclovir hydrochloride)

Chemical name: L-valine, 2-[(2-amino-1, 6-dihydro-6-oxo-9H-purin-9-yl)

Molecular formula: C13H20N6O4•HCl

Molecular mass: 360.80

Structural formula:

[figure not shown]

Figure 2

Physicochemical properties:

Valacyclovir hydrochloride is a white to off-white powder with a maximum solubility in water of 174 mg/mL at 25°C. Valacyclovir hydrochloride has no distinct melting point. It undergoes rapid decomposition above 200°C. A saturated solution (4.82×10^{-1}) of valacyclovir HCl in distilled water has a pH of 3.5 at 25°C. The pKa values of valacyclovir are pKa1 = 1.90, pKa2 = 7.47, and pKa3 = 9.43.

Mechanism of action:

Valacyclovir is the L-valyl ester and a prodrug of the antiviral drug acyclovir. Valacyclovir hydrochloride is rapidly converted to acyclovir, which has *in vitro* and *in vivo* inhibitory activity against human herpes viruses including HSV-1, HSV-2, and varicella-zoster virus (VZV).

The inhibitory activity of acyclovir is highly selective due to its unique affinity for HSV and VZV-encoded tks. This viral enzyme converts acyclovir into acyclovir monophosphate, a nucleotide analogue. The monophosphate is further converted into diphosphate by cellular guanylate kinase and into triphosphate by a number of cellular enzymes. Once incorporated, acyclovir irreversibly binds to viral DNA polymerase, effectively inactivating the enzyme. Acyclovir triphosphate is a potent inhibitor of all the human herpes virus DNA polymerases studied. Acyclovir is virtually inactive in uninfected cells, because it is preferentially taken up and selectively converted to the active triphosphate form by herpes virus-infected cells. Additionally, the tk of uninfected cells does not effectively use acyclovir as a substrate, and cellular α -DNA polymerase is less sensitive to the effects of acyclovir than viral DNA polymerase.

A combination of the tk specificity, competitive inhibition of DNA polymerase, and incorporation and termination of the growing viral DNA chain results in the inhibition of herpes virus replication. No effect on latent non-replicating virus has been demonstrated. Inhibition of viral replication reduces the period of viral shedding, which limits the degree of spread and level of pathology and facilitates healing. The pain of shingles is related to viral damage to neurons, which takes place during viral replication.

Pharmacokinetics:

Absorption: After oral administration, valacyclovir hydrochloride is rapidly absorbed from the gastrointestinal tract and nearly completely converted to acyclovir and L-valine by first-pass intestinal and/or hepatic metabolism. The absolute bioavailability of acyclovir after administration of valacyclovir hydrochloride is $54.5\% \pm 9.1\%$ as determined following a 1000-mg oral dose of valacyclovir hydrochloride and 350-mg IV acyclovir dose to 12 healthy volunteers. Valacyclovir pharmacokinetics are not dose-proportional. The rate and extent of absorption decreases with increasing dose, resulting in a less than proportional increase in maximum plasma concentration (C_{max}) over the therapeutic dose range and a reduced bioavailability at doses above 500 mg. Acyclovir pharmacokinetics are unaltered after multiple-dose administration.

Distribution: The binding of Valacyclovir to human plasma proteins ranges from 13.5% to 17.9%.

Metabolism: Following absorption, Valacyclovir is rapidly and nearly completely hydrolyzed to acyclovir and L-valine, an essential amino acid, by first-pass metabolism. This hydrolysis is mediated primarily by the enzyme valacyclovir hydrolase and occurs predominantly in the liver.

Elimination: The pharmacokinetic disposition of acyclovir delivered by valacyclovir is consistent with previous experience from intravenous and oral acyclovir. Acyclovir is eliminated primarily by urinary excretion of unchanged drug. In all studies of valacyclovir hydrochloride, the half-life of acyclovir typically averages 2.5 to 3.3 hours in subjects with normal renal function.

Indications and clinical uses:

Valacyclovir in caplet form (as valacyclovir hydrochloride) is indicated:

- For the treatment of herpes zoster (shingles).
- For the treatment or suppression of genital herpes in immunocompetent individuals and suppression of recurrent genital herpes in HIV-infected individuals.
- To reduce the risk of transmission of genital herpes with the use of suppressive therapy. Safer sex practices should be used with suppressive therapy.
- For the treatment of cold sores (herpes labialis).

Geriatrics (> 65 years of age): Use in the geriatric population may be associated with differences in safety due to age-related changes in renal function (a brief discussion can be found in the appropriate sections).

Contraindications:

Valacyclovir is contraindicated in patients with a known hypersensitivity or intolerance to Valacyclovir, acyclovir, or any component of the formulation.

Warnings and precautions:

General care should be taken to ensure adequate fluid intake in patients, particularly geriatric patients, who are at risk of dehydration.

The safety and efficacy of Valacyclovir have not been established for the treatment of disseminated herpes zoster. The safety and efficacy of Valacyclovir have not been established in immunocompromised patients other than for the suppression of anogenital herpes in HIV-infected patients. The safety and efficacy of Valacyclovir for the suppression of recurrent anogenital herpes in patients with advanced HIV disease (CD4 cell count < 100 cells/mm³) have not been established.

- Central nervous system

Central nervous system adverse reactions (e.g., agitation, hallucinations, confusion, and encephalopathy) may occur in both adult and pediatric (> 12 years of age) patients (with or without reduced renal function) and in patients with underlying renal disease who receive higher than recommended doses of Valacyclovir for their level of renal function. Elderly patients are more likely to have central nervous system adverse reactions. Use with caution in elderly patients and reduce dosage in patients with renal impairment.

- Hepatic/biliary/pancreatic

Dose modification is not required in patients with mild or moderate cirrhosis (hepatic synthetic function maintained). Pharmacokinetic data in patients with advanced cirrhosis (impaired hepatic synthetic function and evidence of portal-systemic shunting) do not indicate the need for dosage adjustment. There are no data available on the use of higher doses of Valacyclovir (≥ 4 g daily [QD]) in patients with liver disease. Caution should, therefore, be exercised when administering higher doses of Valacyclovir to these patients.

Renal Renal insufficiency and acute renal failure have been observed in patients taking Valacyclovir at the recommended dosage and/or with no previous renal conditions and may be associated with renal pain. Acyclovir, the active metabolite of Valacyclovir, is eliminated by renal clearance; therefore, the dose of Valacyclovir must be reduced in patients with renal impairment (see Dosage and administration; Patients with acute or chronic renal impairment). Geriatric patients are likely to have reduced renal function and therefore, the need for dose reduction must be considered in this group of patients. Both geriatric patients and patients with a history of renal impairment are at increased risk of developing neurological side effects and should be closely monitored for evidence of these effects. In the reported cases, these reactions were generally reversible on discontinuation of treatment. Cases of acute renal failure have been reported in patients without adequate hydration. Precipitation of acyclovir in renal tubules may occur when the solubility (2.5 mg/mL) is exceeded in the intratubular fluid. Adequate hydration should be maintained for all patients.

Adverse reactions:

Serious Adverse Drug Reactions

- Thrombotic thrombocytopenic purpura (TPP)/hemolytic-uremic syndrome (HUS)
- Acute renal failure
- Central nervous system effects

Adverse Drug Reaction Overview

The most frequent adverse reactions associated with the use of Valacyclovir are headache and nausea. Neurological side effects have also been reported in rare instances. Geriatric patients and patients with a history of renal impairment are at increased risk of developing these effects. In the reported cases, these reactions were generally reversible on discontinuation of treatment.

ENSIGN Clinical Trial Adverse Drug Reactions Because the ENSIGN clinical trial will be conducted under very specific conditions, the adverse reaction rates observed may not reflect the rates observed in practice and should not be compared to the rates in the clinical trials of another drug.

Herpes Zoster: Adverse drug reactions were not significantly different between patients receiving Valacyclovir and those receiving placebo or acyclovir in two double-blind, randomized clinical trials of treatment of herpes zoster (shingles) in immunocompetent patients. The most frequent adverse drug reactions reported in recipients of Valacyclovir are listed in Table 1.

Table 1. Incidence (%) of Drug-Related Adverse Reactions Occurring in ≥ 1% of Patients Receiving Valacyclovir in Two Clinical Trials of Herpes Zoster

Adverse Drug Reaction	Herpes Zoster			
	18–50 Years		> 50 Years	
	Valacyclovir (n=202) (%)	Placebo (n=195) (%)	Valacyclovir (n=765) (%)	Acyclovir (n=376) (%)
Nausea	8	6	12	14
Headache	11	8	8	7
Diarrhea	4	4	4	4
Vomiting	2	2	4	3
Asthenia	1	3	3	2
Constipation	< 1	< 1	3	3
Abdominal pain	< 1	1	2	1
Anorexia	< 1	2	2	2
Dizziness	1	1	2	2
Dry Mouth	< 1	0	2	1
Dyspepsia	0	< 1	2	1
Flatulence	0	0	1	1
Pruritus	1	0	< 1	0

Genital Herpes: In two double-blind, randomized trials of treatment of recurrent genital herpes in immunocompetent patients, adverse drug reactions were not significantly different between patients receiving Valacyclovir and those receiving placebo. The most frequent adverse reactions are listed in Table 2.

Table 2. Incidence (%) of Drug-Related Adverse Reactions Occurring in ≥ 1% of Patients Receiving Valacyclovir in Two Clinical Trials of Treatment of Recurrent Genital Herpes

Adverse Drug Reaction	Valacyclovir (n=1235) (%)	Placebo (n=439) (%)
Headache	11	9
Nausea	5	6
Diarrhea	4	4
Dizziness	2	2

Abdominal pain	2	1
Asthenia	1	3

Cold Sores: Adverse drug reactions reported by patients receiving 2000 mg Valacyclovir twice daily (n=609) or placebo (n=609) for one day in clinical studies of treatment of cold sores are listed below.

Table 3. Incidence (%) of Drug-Related Adverse Reactions Occurring in $\geq 1\%$ of Patients Receiving Valacyclovir in Two Clinical Trials of Treatment of Cold Sores

Adverse Drug Reaction	Valacyclovir (n=609) (%)	Placebo (n=609) (%)
Headache	9	5
Nausea	4	5
Diarrhea	3	3
Dyspepsia	1	1

Abnormal hematologic and clinical chemistry findings: In herpes zoster trials, the frequency of WBC abnormality (< 0.75 times the lower limit of normal) was 1.3% for patients receiving Valacyclovir compared with 0.6% for patients receiving placebo. This difference was not clinically or statistically significant.

In clinical studies of treatment of cold sores, the frequencies of abnormal ALT values ($> 2 \times \text{ULN}$) were 1.8% for patients receiving Valacyclovir at the recommended clinical dose and 0.8% for patients receiving placebo. Other laboratory abnormalities (hemoglobin, WBCs, alkaline phosphatase, and serum creatinine) occurred with similar frequencies in the two groups.

Post-market adverse drug reactions: The following events have been reported voluntarily during post-approval use of Valacyclovir in clinical practice. These events have been chosen for inclusion due to either their seriousness, frequency of reporting, causal connection to Valacyclovir, or a combination of these factors. Post-market AEs are reported spontaneously from a population of unknown size, thus estimates of frequency cannot be made. Allergic: Acute hypersensitivity reactions including anaphylaxis, angioedema, dyspnea, pruritus, rash, and urticaria. Central Nervous System Symptoms: Headache. Reports of neurological reactions including dizziness, confusion, hallucinations (auditory and visual), aggressive behavior, decreased consciousness, tremor, ataxia, dysarthria, convulsions, encephalopathy, coma, mania, and seizures. Agitation and psychotic symptoms have also been reported. These events are generally reversible and usually seen in patients with renal impairment or other predisposing factors. General: Facial edema, hypertension, and tachycardia. Gastrointestinal: Nausea, abdominal discomfort, vomiting, and diarrhea. Hematological: Reports of thrombocytopenia, aplastic anemia, leukocytoclastic vasculitis, and TTP/HUS. Leukopenia has mainly been reported in immunocompromised patients. Hepatobiliary Tract and Pancreas: Reports of reversible increases in liver function test and hepatitis. Ophthalmologic: Visual abnormalities. Renal: Reports of renal impairment, elevated blood creatinine and BUN, acute renal failure, renal pain, and hematuria. Renal pain may be associated with renal failure. Skin: Erythema multiforme and rashes including photosensitivity. Other: There have been reports of renal insufficiency, microangiopathic hemolytic anemia, and thrombocytopenia (sometimes in combination) in severely immunocompromised patients, particularly those with advanced HIV disease, receiving high doses (8000 mg QD) of Valacyclovir for prolonged periods in clinical trials. These findings have also been observed in patients not treated with Valacyclovir who have the same underlying or concurrent conditions.

Drug interactions:

No clinically significant interactions have been identified. No dosage adjustment is recommended when Valacyclovir is coadministered with digoxin, antacids, thiazide diuretics, cimetidine, or probenecid in subjects with normal renal function.

Cimetidine and probenecid increase the area under the curve (AUC) of acyclovir and reduce acyclovir renal clearance after Valacyclovir administration (1000 mg). However, no dosage adjustment is necessary at this dose because of the wide therapeutic index of acyclovir.

Drug-Food Interactions: There is no known interaction with food.

Drug-Herb Interactions: Interactions with herbal products have not been established.

Drug-Laboratory Test Interactions: Interactions with laboratory tests have not been established.

Dosage and administration:

The recommended dose for the ENSIGN trial is 2 g orally t.i.d. for 14 days (day 1 to day 15). This dose has been calculated to give a similar AUC as 10 mg/kg of intravenous acyclovir administered every 8 hours. This is the same dose regimen used in a previous phase I clinical trial of ADV/HSV-tk plus acyclovir and topotecan in patients with recurrent ovarian cancer.⁸¹ NOTE: For patients with serum creatinine level between 1.6–2.0 × ULN, valacyclovir dose will be reduced 50% (i.e., 1 g t.i.d.).

Recommended Dose and Dosage Adjustment

Patients who develop signs of TTP/HUS or neurotoxicity (e.g., encephalopathy, seizures) will be removed from treatment.

Patients with acute or chronic renal impairment: Caution is advised when administering Valacyclovir to patients with impaired renal function. Adequate hydration should be maintained.

Pharmacokinetic and safety evaluations following administration of oral valacyclovir hydrochloride have been performed in patients with renal impairment and volunteers with end-stage renal disease managed by hemodialysis. Valacyclovir dosing in patients with renal impairment is shown in Table 4.

Table 4. Valacyclovir dosing in patients with renal impairment

Creatinine Clearance (mL/min)				
	> 50	30 to <50	10 to <30	< 10
Herpes Zoster	1000 mg every 8 hours†	1000 mg every 12 hours	1000 mg every 24 hours	500 mg every 24 hours
Recurrent Episodes of Genital Herpes	500 mg every 12 hours†	500 mg every 12 hours†	500 mg every 24 hours	500 mg every 24 hours
Suppression of genital herpes for immunocompetent patients	1000 mg every 24 hours†	1000 mg every 24 hours†	500 mg every 24 hours	500 mg every 24 hours
Alternate dose for immunocompetent patients with less than or equal to 9 recurrences/year	500 mg every 24 hours†	500 mg every 24 hours†	500 mg every 48 hours	500 mg every 48 hours
HIV-infected patients	500 mg every 12 hours†	500 mg every 12 hours†	500 mg every 24 hours	500 mg every 24 hours
Initial Episode of Genital Herpes	1000 mg every 12 hours†	1000 mg every 12 hours†	1000 mg every 24 hours	500 mg every 24 hours
Cold Sores (Herpes Labialis)§	Two 2000 mg doses taken 12 hours apart†	Two 1000 mg doses taken 12 hours apart	Two 500 mg doses taken 12 hours apart	500 mg single dose

†Standard dose - adjustment not necessary

§Do not exceed one day of treatment.

Overdosage:

Activated charcoal may be administered to aid in the removal of unabsorbed drug. General supportive measures are recommended. Acute renal failure and neurological symptoms, including confusion, hallucinations, agitation, decreased consciousness and coma, and nausea and vomiting may also occur. Caution is required to prevent inadvertent overdose. Many of the reported cases involved renally impaired and geriatric patients receiving repeated overdoses due to lack of appropriate dosage reduction.

Drug interactions:

Cimetidine and Probenecid: Coadministration of probenecid with IV acyclovir has been shown to increase the mean elimination half-life and AUC of acyclovir, leading to corresponding reductions in acyclovir urinary excretion and renal clearance. The administration of cimetidine and probenecid, alone or in combination, reduced the rate

but not the extent of Valacyclovir conversion to acyclovir. Reductions in the renal clearance of acyclovir were observed, resulting in higher acyclovir plasma concentrations. In volunteers with normal renal function, the renal clearance of acyclovir was reduced by approximately 22% and 33% with concomitant cimetidine and probenecid administration, respectively. Renal clearance of acyclovir was reduced by approximately 46% in patients receiving cimetidine, probenecid, and valacyclovir hydrochloride.

An additive increase in acyclovir AUC with concomitant administration of valacyclovir hydrochloride, cimetidine, and probenecid has also been observed. Acyclovir Cmax was increased $8.4\% \pm 27.8\%$, $22.5\% \pm 25.3\%$, and $29.6\% \pm 27.5\%$ by cimetidine, probenecid, and combination treatment (concomitant cimetidine and probenecid administration), respectively. Acyclovir AUC (0 to 24 hours) was increased $31.9\% \pm 22.9\%$, $49.0\% \pm 27.9\%$, and $77.9\% \pm 38.6\%$ by cimetidine, probenecid, and combination treatment, respectively. Digoxin: The pharmacokinetics of digoxin (two 0.75 mg doses, 12 hours apart) were not affected by multiple-dose administration of Valacyclovir (1000 mg every 8 hours for 8 days beginning 12 hours before digoxin dosing) in a study with 12 volunteers. Acyclovir pharmacokinetics after single-dose administration of Valacyclovir (1000 mg) remained unchanged when the same dose was administered immediately after the second of two 0.75 mg doses of digoxin given 12 hours apart. Antacids: The administration of an aluminum hydroxide and magnesium hydroxide-containing antacid either 30 minutes before or 65 minutes after administration of 1000 mg Valacyclovir had no effect on the pharmacokinetics of acyclovir in a study with 18 volunteers. Thiazide diuretics: Thiazide diuretics did not affect acyclovir pharmacokinetics after administration of valacyclovir hydrochloride in a geriatric population.

Storage and stability:

Valacyclovir should be stored between 15° and 30°C and protected from light.

Dosage forms, composition, and packaging: Valacyclovir 500 mg caplets are blue, film-coated, capsule-shaped tablets printed with "Valacyclovir 500 mg". Each blue caplet contains valacyclovir hydrochloride equivalent to 500 mg Valacyclovir and the inactive ingredients carnauba wax, cellulose, crospovidone, hydroxypropyl methylcellulose, Indigotine Aluminum Lake, magnesium stearate, polyethylene glycol, polysorbate 80, povidone, silicon dioxide, and titanium dioxide. The blue, film-coated caplets are printed with edible white ink. Valacyclovir 1000 mg caplets are white, film-coated, capsule-shaped tablets engraved with "GX CF2". Each white caplet contains valacyclovir hydrochloride equivalent to 1000 mg valacyclovir and the inactive ingredients carnauba wax, cellulose, crospovidone, hydroxypropyl methylcellulose, magnesium stearate, polyethylene glycol, polysorbate 80, povidone, silicon dioxide, and titanium dioxide. The white, film-coated caplets are engraved. The 500 mg and 1000 mg caplets are available in blister packs of 30 and 21 caplets, respectively.

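### Section 9.2's advice that valacyclovir needs no adjustment with cimetidine or probenecid is supported only at 1000 mg in normal renal function, which is not how the trial uses the drug

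*Combined protocol and SAP*

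**What the plan says.** The first Drug interactions paragraph of Section 9.2 gives general advice: "No dosage adjustment is recommended when Valacyclovir is coadministered with digoxin, antacids, thiazide diuretics, cimetidine, or probenecid in subjects with normal renal function". It goes on to say that cimetidine and probenecid raise acyclovir AUC and lower its renal clearance after a 1000 mg dose, and concludes: "However, no dosage adjustment is necessary at this dose because of the wide therapeutic index of acyclovir".

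The second Drug interactions paragraph gives the sizes. In volunteers with normal renal function, "the renal clearance of acyclovir was reduced by approximately 22% and 33% with concomitant cimetidine and probenecid administration, respectively". For the two together: "Renal clearance of acyclovir was reduced by approximately 46% in patients receiving cimetidine, probenecid, and valacyclovir hydrochloride". It also gives the AUC and Cmax rises.

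Under Dosage and administration, the trial dose is 2 g three times daily for 14 days (day 1 to day 15), chosen to match the AUC of 10 mg/kg of intravenous acyclovir every 8 hours. It is halved to 1 g three times daily when creatinine is 1.6 to 2.0 x ULN. Section 8.1 admits creatinine below 2 x ULN.

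The renal warning in Section 9.2 requires a lower dose in renal impairment because acyclovir is cleared by the kidney. Section 10 restricts other anticancer treatment only. It says concomitant therapies will be monitored but names no action for cimetidine or probenecid.

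**The concern.** The only interaction advice in the protocol tells sites to leave the dose alone, and its support stops short of the trial's regimen. A site that follows it would keep a patient on the full 2 g while one or both drugs slow acyclovir clearance. Elsewhere the protocol treats slower renal clearance as a reason to give less.

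What is at stake is avoidable acyclovir exposure over two weeks. Section 9.2 lists acute renal failure and central nervous system effects among the serious reactions. On overdose it notes: "Many of the reported cases involved renally impaired and geriatric patients receiving repeated overdoses due to lack of appropriate dosage reduction".

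Scheduled monitoring would not reliably catch a problem in time. Chemistry is due on day 0 and next on day 17, after the course ends. The 5-day visit window could bring that test forward to day 12 at the earliest, and other tests are done only when clinically indicated. Section 9.1 lists raised creatinine as a possible effect of the vector injected on day 0, so renal function may shift during this interval.

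**Working it through.** The point rests mainly on the scope of the text. There is no stated figure to reproduce.

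**Step 1. Scope of the advice against use in the trial.** The protocol does not define normal renal function. I assume that creatinine above ULN falls outside it.

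| Patients | Dose | Within 1000 mg? | Within normal renal function? |
|---|---|---|---|
| Creatinine at or below ULN | 2 g t.i.d. | No | Yes |
| Above ULN, below 1.6 x ULN | 2 g t.i.d. | No | No |
| 1.6 to 2.0 x ULN (entry below 2.0) | 1 g t.i.d. | Yes, per dose | No |

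Under the creatinine-based dosing rule, no group meets both limits.

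**Step 2. Does anything else in Section 9.2 fill the gap?** Table 4 marks several doses "Standard dose - adjustment not necessary", including those for creatinine clearance above 50 mL/min. These are labelled herpes doses, with no interacting drug. The only 2000 mg dose in the table is for cold sores: two doses 12 hours apart, for no more than one day. The trial gives 3 x 2 g = 6 g a day for 14 days. The protocol supports the regimen by earlier use ("This is the same dose regimen used in a previous phase I clinical trial"), but does not say that those patients took cimetidine or probenecid.

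**Step 3. Size of the interaction, and whether the two sets of figures agree.** If the clearance fall were the whole mechanism, the AUC rise would be 1/(1 - fall) - 1.

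- Cimetidine: 1/(1 - 0.22) - 1 = 28.2%; stated 31.9%.
- Probenecid: 1/(1 - 0.33) - 1 = 49.3%; stated 49.0%.
- Both: 1/(1 - 0.46) - 1 = 85.2%; stated 77.9%.

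The figures are broadly consistent. Moving each AUC rise by its reported plus-or-minus value (type not stated) gives:

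- Cimetidine: 31.9 - 22.9 = 9.0% to 31.9 + 22.9 = 54.8%.
- Probenecid: 49.0 - 27.9 = 21.1% to 49.0 + 27.9 = 76.9%.
- Both: 77.9 - 38.6 = 39.3% to 77.9 + 38.6 = 116.5%.

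Mean Cmax rises are smaller: 8.4%, 22.5% and 29.6%.

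**Step 4. Illustration at the trial dose.** The protocol does not test whether the same proportional rises hold at 2 g. If they did, the targeted AUC of 10 mg/kg intravenously every 8 hours would become that of about 10 x 1.319 = 13.2, 10 x 1.490 = 14.9 or 10 x 1.779 = 17.8 mg/kg. The conclusion does not depend on this step.

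**The case against.** The strongest reply is that both limits are already printed, a sentence or two apart, and that the protocol never claims the advice extends to 2 g or to raised creatinine. The text is general product information, kept apart from the trial's own dosing rule, and its source may cover higher doses. This stands in part: the protocol misstates nothing, and the gap is one of coverage. But the paragraph ends in an instruction not to adjust, and no trial-specific instruction replaces it.

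Safeguards also exist: hydration, closer observation of geriatric and renally impaired patients, removal for neurotoxicity or TTP/HUS, chemistry when clinically indicated, and monitoring of concomitant therapy. They reduce the risk. However, removal acts after the event, and monitoring a co-medication does not tell the site what to do about it.

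A reader might go further and treat 1.6 x ULN as an exposure limit, then convert each clearance fall into an equivalent creatinine. The documents do not support that. The 1.6 x ULN figure is a creatinine band and is nowhere described as an acyclovir exposure threshold. The conversion would need clearance to vary inversely with creatinine, ULN to be the reference point, and a drug-induced fall to act like renal impairment. The 22% and 33% come from volunteers with normal renal function, and the 46% from patients whose renal function is not stated.

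A reader might also infer that valacyclovir should be halved for anyone on these drugs, or that creatinine at ULN should be the cut-off for allowing them. Neither is derivable from the documents. Valacyclovir is the prodrug on which the gene therapy depends, and its dose was set to an AUC target, so halving it could cost activity.

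**Conclusion.** The point holds as a gap in coverage. The advice is supported only at 1000 mg in normal renal function, while the trial gives 2 g three times daily, in part to patients with raised creatinine, and has no rule for the two drugs. The reported mean AUC rises of 31.9% to 77.9% are large enough to deserve an instruction, given that the protocol itself lowers the dose when renal clearance falls.

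It would be wrong to conclude that 2 g with either drug is unsafe. The documents contain no exposure or outcome data for that combination, and Section 9.2 describes acyclovir's therapeutic index as wide. Nor do they say how many of the planned 25 patients (16 + 9) would take either drug; that use is uncommon is my assumption. The reading of raised creatinine as outside normal renal function is also an assumption, but the dose limit applies without it.

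This is a cheap improvement to dosing safety. It has no bearing on the sample size or the primary analysis.

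**What to change.** In Section 9.2, add a sentence after the interaction advice saying that it was established at 1000 mg in normal renal function and does not cover the trial dose or patients with raised creatinine.

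In Section 10, add that cimetidine and probenecid are to be paused or switched to an alternative from day 0 to day 15. Have the study coordinator check for both when dispensing valacyclovir on day 0. Leave the existing creatinine-based reduction as it is, and add no dose reduction for co-medication.

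The cost is one sentence, one rule and one check at a visit that already takes place. The downside is that a few patients pause or switch a drug for about two weeks.

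### The trial's valacyclovir dose has only a serum-creatinine rule, while the plan's own warnings call for reduction in renal impairment without a threshold or amount for 6 g/day

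*Combined protocol and SAP*

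**What the plan says.** Section 6, Section 9.2 (Dosage and administration), the treatment footnote in Section 11 and Section 12 all give the same dose, 2 g three times daily, and the same rule. In the words of Section 9.2: "For patients with serum creatinine level between 1.6–2.0 × ULN, valacyclovir dose will be reduced 50" per cent, that is, to 1 g three times daily. Section 8.1 requires serum creatinine below 2 × ULN. None of these places sets a clearance limit or asks for clearance to be calculated.

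The warnings in Section 9.2 are broader:

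- Central nervous system: "Use with caution in elderly patients and reduce dosage in patients with renal impairment".
- Renal: "the dose of Valacyclovir must be reduced in patients with renal impairment", with a pointer to the dosage text on renal impairment.
- Geriatric patients, also under Renal: "the need for dose reduction must be considered in this group of patients".

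The dosage text pointed to advises caution and hydration, and then states: "Valacyclovir dosing in patients with renal impairment is shown in Table 4". Table 4 lists herpes zoster, genital herpes, HIV and cold-sore regimens by clearance band. It has no row for 2 g three times daily.

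On the choice of dose, Section 9.2 says: "This dose has been calculated to give a similar AUC as 10 mg/kg of intravenous acyclovir administered every 8 hours".

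**The concern.** An investigator is told to reduce the dose in renal impairment but has a number to act on only from 1.6 × ULN upwards. Creatinine depends on age, sex and body size as well as on renal function, so a fixed multiple of ULN can miss low clearance in older or lighter patients. Such patients are to be expected: there is no upper age limit, and in the previously treated NSCLC trials described in Section 1.1, 42% to 50% of patients were 65 or older and 7% to 14% were 75 or older.

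The stake is patient safety. Section 9.2 links neurological reactions to renal impairment, older age and doses too high for renal function. It names acute renal failure as a serious reaction, and under Overdosage it attributes many cases to missing dose reduction in renally impaired and geriatric patients. The full 14-day supply is dispensed on day 0, and the next scheduled chemistry is nominally on day 17.

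**Working it through.** **The plan's own figure.** 2 g × 3 = 6 g/day. Half of that is 3 g/day, or 1 g three times daily, as stated.

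**Clearance at creatinine values the rule leaves at full dose.** The documents give no formula, ULN or weights, so these are assumed: Cockcroft-Gault; ULN 1.2 to 1.3 mg/dL for men and 1.0 to 1.1 mg/dL for women; ages and weights as listed.

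Clearance = (140 − age) × weight / (72 × creatinine), × 0.85 for women. Setting clearance to 50 gives creatinine = (140 − age) × weight [× 0.85] / 3600, which is then divided by ULN. For a 65-year-old, 70 kg man: 75 × 70 / 3600 = 1.458 mg/dL; 1.458/1.3 = 1.12 and 1.458/1.2 = 1.22.

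| Assumed patient | Creatinine at 50 mL/min (mg/dL) | As multiple of ULN | Clearance at 1.5 × ULN (mL/min) |
|---|---|---|---|
| Man 65, 70 kg | 1.458 | 1.12–1.22 | 37.4–40.5 |
| Man 75, 70 kg | 1.264 | 0.97–1.05 | 32.4–35.1 |
| Woman 65, 60 kg | 1.063 | 0.97–1.06 | 32.2–35.4 |
| Woman 75, 60 kg | 0.921 | 0.84–0.92 | 27.9–30.7 |
| Man 50, 70 kg | 1.750 | 1.35–1.46 | 44.9–48.6 |
| Man 65, 90 kg | 1.875 | 1.44–1.56 | not needed |
| Man 50, 90 kg | 2.250 | 1.73–1.88 | not needed |

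In six of the seven cases clearance reaches 50 mL/min before the creatinine rule acts. In the seventh the rule acts first. With 2160 (72 × 30) as the divisor, only the 75-year-old, 60 kg woman reaches 30 mL/min before 1.6 × ULN, at 1.40 to 1.53. The 65-year-old woman gets there at 1.61 to 1.77, the 75-year-old man at 1.62 to 1.76 and the 65-year-old, 70 kg man at 1.87 to 2.03.

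**What Table 4 does at these clearances** (daily dose as a share of that row's standard dose):

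- 30 to below 50 mL/min: zoster 2000/3000 = 67%; cold sores 2000/4000 = 50%; the other five rows 100%. The two rows that are cut have the highest standard doses.
- 10 to below 30 mL/min: zoster 1000/3000 = 33%; cold sores 1000/4000 = 25%; the other five rows 50%.

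**Exposure.** The Drug interactions text gives renal-clearance reductions of 22% with cimetidine and 33% with probenecid; for the two together, "Renal clearance of acyclovir was reduced by approximately 46% in patients receiving cimetidine, probenecid, and valacyclovir hydrochloride". In the same three settings, "Acyclovir AUC (0 to 24 hours) was increased" by 31.9%, 49.0% and 77.9% (SDs 22.9, 27.9 and 38.6). If AUC varies inversely with clearance, the rise is 1/(1 − r) − 1:

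- r = 0.22: 28.2%, against 31.9% observed
- r = 0.33: 49.3%, against 49.0%
- r = 0.46: 85.2%, against 77.9%

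The fit is close. If the same scaling held in renal impairment at 2 g (an assumption), half the normal clearance would give 1/0.5 = 2.0 times the target AUC at full dose, and 0.5/0.5 = 1.0 times at half dose.

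**The case against.** The strongest reply is that the warnings are protocol text. Read as binding, they already oblige an investigator to reduce the dose in a renally impaired patient below 1.6 × ULN. A reader might infer that every such patient receives 6 g/day whatever the clearance; the documents do not support that. What is missing is the threshold and the amount. If instead the warnings are background taken from the prescribing information, the creatinine rule may be how the trial means to meet them. It still misses the low-clearance cases above.

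Other safeguards count. The treating physician may exclude unsafe patients (Sections 7 and 12). Section 9.2 asks for hydration and for close watch of geriatric patients and those with a renal history. Section 15.1 has a run-in of 3 to 6 patients per cohort with a 5-week stagger, and Section 12.4 withdraws patients for neurotoxicity. These lower the risk, but none sets the starting dose.

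Some evidence is reassuring. Section 9.2 calls the neurological reactions generally reversible and says the regimen was used in an earlier phase I trial. Section 9.1 describes valacyclovir with the vector in 59 men of median age 68, without giving the dose, and reports no significant toxicity in previous trials. Acyclovir's wide therapeutic index is cited against adjusting for the cimetidine and probenecid interaction, but at 1000 mg and, in the parallel statement, for normal renal function.

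It would also be tempting to say that full dosing will double the intended AUC. That extrapolates from three interaction points with wide SDs, in data tied to normal renal function, to renal impairment at a higher dose. It shows direction, not size.

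**Conclusion.** The point stands as a gap between the warnings and the dosing rule. The only numeric renal adjustment for 6 g/day is serum creatinine of 1.6 to 2.0 × ULN; the warnings that go further cannot be applied to this regimen as written, and Table 4 does not fill the gap. Full dose at a clearance below 50 mL/min is plausible in older or lighter patients, and below 30 occasionally (one of seven assumed cases). This rests on Cockcroft-Gault and on assumed ULN, ages and weights. How many of the 25 planned patients (16 + 9) would be affected cannot be derived, and the size of any excess exposure is an assumption.

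This is a safety and dosing matter worth correcting. A reader might infer damage to the efficacy analysis. There is none: the power calculation uses sample size, null and target ORR and alpha, and neither it nor the ORR definition depends on this rule.

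**What to change.** Amend Sections 6, 8.1, 9.2, 11 and 12 as follows:

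- Calculate creatinine clearance at screening from age, sex, weight and creatinine, and recheck it with the day 0 chemistry before the vector is injected.
- Give 1 g three times daily if clearance is 30 to below 50 mL/min or creatinine is at least 1.6 × ULN. The 50 cut-point follows Table 4's two highest-dose rows only, so the sponsor and pharmacist should confirm it.
- Make clearance below 30 mL/min an exclusion. Every Table 4 row is cut there, and settling this before injection avoids giving a patient the vector and then withholding the prodrug.
- Label Table 4 as herpes labelling, not trial dosing.

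I would not add an on-treatment creatinine hold: scheduled chemistry is nominally on days 0 and 17, so nothing scheduled would trigger it during dosing.

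The cost is amendment wording and one calculated field, with no new test. A few patients would receive less valacyclovir or become ineligible, which matters somewhat in cohorts of 16 and 9. For example, the assumed 75-year-old, 60 kg woman with creatinine at ULN has a clearance of 42 to 46 mL/min and would move to 1 g three times daily. Her exposure should fall by less than half, because Section 9.2 says absorption is proportionally lower at higher doses.
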